### INTERVENTION AND CONTROL

The control group will receive standard preoperative care only, while the intervention group will receive standard preoperative care plus VR. Standard preoperative care will include the preparation of the preoperative surgical site, preoperative bathing, preoperative hair removal, wearing theater gown, remove all jewelry, correct patient ID bracelet, and complete patient preoperative checklist and health record.

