The Leiden Perioperative Patient Satisfaction questionnaire (LPPSq) is a valid and reliable tool used to assess and measure different aspects of patient satisfaction with perioperative care (Caljouw, Van Beuzekom, & Boer, 2008). This questionnaire consists of 39 questions which are divided over six dimensions; (1) information provision (four questions), (2) discomfort and needs (seven questions), (3) fear and concern (seven questions), (4) professional competence (four questions), (5) staff -patient relationship (14 questions), and (6) service quality (three questions). Patient satisfaction with

Study Protocol

perioperative care will be expressed by the mean satisfaction scores and the percentage of the maximum possible scores for each dimension (Caljouw et al., 2008). The participants will be asked to complete the questionnaire 24 hours after surgery before they are discharged (T4). This outcome will be collected by a research assistant at the research site, King Abdulaziz University Hospital.

4- Hospital Length of Stay (LOS) as measured from the date of admission to discharge from hospital.

The hospital length of stay is a proven recovery time indicator that can be used as a valid measure of robust outcomes in a variety of surgical fields and medical conditions (Laderman & Mate, 2016). The LOS will be measured in days that recorded on patients' discharge summary by subtracting the date of admission to hospital from the date of discharge from hospital (Abdelhak, Grostick, & Hanken, 2014). This outcome will be collected by a research assistant at the research site, King Abdulaziz University Hospital.

5- Adverse effect of VR intervention at any time point as measured by the Virtual Reality Symptom Questionnaire (VRSQ)

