The Virtual Reality Symptom Questionnaire (VRSQ) is a valid and reliable measure used to evaluate the possible occurrence of symptoms of cybersickness, a type of motion sickness caused by exposure to VR (Sevinc & Berkman, 2020). This questionnaire assesses eight general physical side effects, (1) general discomfort, (2) fatigue, (3) boredom, (4) drowsiness, (5) headache, (6) dizziness, (7) concentration difficulties, and (8) nausea. It also assesses five visual effects (1) tired eyes, (2) aching eyes, (3) eyestrain, (4) blurred vision, and (5) difficulties focusing on a seven-point range from 0 to 6, with 0 indicating that the symptom is not present and 6 that the symptom is severe. The potential participants in the intervention group will be asked to complete the questionnaire immediately before surgery (T2). This outcome will be collected by the PhD candidate.

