## BLINDING

The Research Assistant involved in outcome data collection will be blinded to the group allocation, as will the statistician who will conduct the analysis. Clinicians (nurses, doctors, and other healt h providers) will not be told who is participating in the study nor their group allocation; however, it is acknowledged that it is not possible to prevent participants from sharing this information with them.

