# SAMPLE SIZE

Based on the previous study of Bekelis et al. (2017), a sample of 150 participants (75 per group) will give the study 80% power to detect a moderate effect size of 0.5 standard deviations between groups in the primary outcome variable, with a type 1 error rate of 5%. This calculation assumes a dropout rate of 15%.

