# STATISTICAL PLAN

Characteristics of groups will be summarised using counts and percentages for categorical variables and means and standard deviations for continuous variables. The primary outcome will be compared between groups at each follow-up time points using a linear mixed effects regression model, with fixed effects including treatment arm time (categorical), the interaction between treatment and time, and the baseline value of the outcome variable. Differences in mean VAS anxiety scores

between groups at each time point will be presented together with 95% confidence intervals and pvalue. Continuous secondary outcomes with repeated measurements will be compared using the same model. Hospital length of stay will be compared using the rank-sum test. Patient satisfaction and the VRSQ will be compared between groups using an independent sample t-test.

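### The VR symptom questionnaire is assigned to the VR arm alone, yet the plan tests it between arms, so the named t-test cannot be computed

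*Protocol*

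**What the plan says.** Under Secondary Outcomes, the protocol introduces the fifth outcome as "Adverse effect of VR intervention at any time point as measured by the Virtual Reality Symptom Questionnaire (VRSQ"). The description that follows lists eight general and five visual symptoms, each scored 0 to 6, and says who completes the form and when: "The potential participants in the intervention group will be asked to complete the questionnaire immediately before surgery (T2"). On who collects it: "This outcome will be collected by the PhD candidate".

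The schedule of assessments marks VR adverse effects at t2 only and does not name an arm.

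The section on intervention and control states: "The control group will receive standard preoperative care only, while the intervention group will receive standard preoperative care plus VR".

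The Statistical Plan states: "Patient satisfaction and the VRSQ will be compared between groups using an independent sample t-test".

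The Blinding section states: "The Research Assistant involved in outcome data collection will be blinded to the group allocation, as will the statistician who will conduct the analysis".

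**The concern.** The collection rule yields data in one arm, and the analysis rule needs data in two. Both are stated outright, so this is a contradiction rather than a detail left for later. A statistical analysis plan, which is not at hand, could drop the test. It could not supply control scores that were never collected, and symptoms at T2 cannot be recovered once the patient has gone to theatre.

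Interpretation is also at stake. Several VRSQ items, such as fatigue, headache, drowsiness and nausea, may occur in a patient awaiting surgery without any VR. The trial enrols only patients with an APAIS anxiety score of 11 or more, in whom such complaints are plausible. The VRSQ is not given at T1 either, so the single T2 score has neither a baseline nor a control group to be read against. It is the only adverse-effect outcome in the outcome table.

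Two smaller matters follow. The outcome's title covers any time point, while collection is at T2 only. And a form present in one arm alone could show which arm is which if it travels with the rest of the data.

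**Working it through.** **The plan's own figure.** The protocol says "a sample of 150 participants (75 per group) will give the study 80% power" for a difference of 0.5 SD in the primary outcome, with 5% type 1 error and 15% dropout. Taking the test as two-sided (the sidedness is not stated):

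- n per arm = 2 × (1.960 + 0.842)² / 0.5² = 62.8, rounded up to 63.
- Allowing for dropout: 63 / 0.85 = 74.1, rounded up to 75 per arm, 150 in total.

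The stated figure is reproduced. It concerns the primary outcome and does not depend on the VRSQ.

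**The planned VRSQ test.**

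| Item | VR arm | Control arm | Protocol section |
|---|---|---|---|
| Randomised | 75 | 75 | Sample Size |
| Asked to complete the VRSQ at T2 | yes | not stated anywhere | Secondary Outcomes |
| VRSQ scores available, at most | 75 | 0 | follows from the two rows above |
| Needed for the planned test | at least some | at least some | Statistical Plan |

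The two-sample t statistic is (mean in VR arm − mean in control arm) / [s × √(1/n₁ + 1/n₂)]. With n₂ = 0 the control mean does not exist and 1/n₂ is undefined. Running the test with 75 values against none returns no statistic, no degrees of freedom and no p-value.

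**Is the one-arm reading fair?** For cortisol, heart rate, pain and satisfaction, the Secondary Outcomes section refers to participants without naming an arm. Only for the VRSQ does it name the intervention group. Those other outcomes go to the Research Assistant, who is to be blinded; the VRSQ goes to the PhD candidate. Both features fit a form meant for the VR arm.

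**What each repair would deliver.** These figures describe the repairs, not the size of the flaw.

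- Form length: 8 general + 5 visual = 13 items.
- Both arms, 75 each: detectable difference at 80% power, two-sided 5%, is (1.960 + 0.842) × √(2/75) = 0.46 SD. If 15% were lost, leaving 75 × 0.85 ≈ 64 per arm, it would be 0.50 SD.
- VR arm only: 95% confidence half-width for the mean score is t(0.975, 74) / √75 = 0.23 SD, or 0.25 SD with 64.
- VR arm only, one symptom as a proportion: the half-width is largest at 50%, where it is 1.96 × √(0.25/75) = 0.113, or about 11 percentage points.

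The 15% is the dropout assumed for the primary outcome. Nothing ties it to a form completed on the day of allocation, so 64 is only an illustrative lower case.

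The share of symptoms present without VR is not in the protocol, so the size of any misattribution cannot be calculated.

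**The case against.** The strongest reply is that the collection sentence names the intervention group but does not say it alone, and that the schedule names no arm. The Statistical Plan might then show that two-arm collection was intended. This is possible, but the wording makes it the less likely reading. It does not remove the problem: staff following the collection sentence would not hand the form to controls, whatever the analyst expected.

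Second, the error reveals itself. A test with an empty arm gives no answer rather than a false one, and it affects the last of five secondary outcomes. That stands, and it limits the seriousness of the point.

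Third, describing cybersickness in the exposed arm alone is a legitimate design. That also stands, provided the between-arm test is dropped and the symptoms are not all credited to VR.

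A reader might infer more than the document supports in two respects:

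- *That the statistician is necessarily unblinded.* The protocol does not say how or when VRSQ data reach the statistician. They are collected separately by the PhD candidate and could be held in a separate file. Allocation would be revealed only if participant-level VRSQ data were supplied with the other outcomes before the blinded analyses were finished.
- *That VR safety goes unwatched.* The Risk and Benefits section provides for continuous monitoring by the researcher and a response to side effects. What is missing is an analysable comparison, not surveillance.

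**Conclusion.** The contradiction between Secondary Outcomes and the Statistical Plan is real, and nothing else in the protocol resolves it. As written, the planned VRSQ comparison has at most 75 observations against 0 and cannot be computed. This rests on reading the collection sentence as excluding controls, which its wording and the choice of collector support.

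The limit on interpretation also holds: one post-exposure score in one arm cannot separate VR effects from background preoperative symptoms. How much this matters depends on a background rate that the protocol does not give.

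The risk to the statistician's blinding is conditional on how the data are handled. The mismatch between the outcome's title and its single time point is a matter of wording.

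This should be fixed, but it is not a defect that threatens the trial's main result. The primary outcome, its model, the randomisation and the sample size are untouched.

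**What to change.** Reconcile the VRSQ paragraph with the Statistical Plan before recruitment, in one of two ways.

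1. **Preferred: collect in both arms.** Give the same 13 symptom items to controls at T2 and keep the between-group comparison. State who collects them: the PhD candidate, now named as collector, is not stated to be blinded, which matters for self-reported symptoms. The cost is a short form for about 75 controls and a protocol change needing ethics review.
2. **Otherwise: keep one arm.** Delete the VRSQ t-test. Report each symptom in the VR arm descriptively with a 95% confidence interval, and state that these symptoms cannot all be attributed to VR. Keep the VRSQ data out of the statistician's dataset until every blinded between-group analysis, secondary as well as primary, is complete. Releasing them after the primary analysis alone would leave cortisol, heart rate, pain, satisfaction and length of stay exposed. The cost is a small change to the Statistical Plan and a data-handling step.

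Under either option, align the outcome's title with the T2-only collection given in its description and in the schedule, and have the schedule name the arm or arms that complete the form.

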# Summary of Outcomes variables and Measures:

Variable	Scales/Questionnaires/instruments
Primary outcome	
Perioperative anxiety	Visual Analog Scale for Anxiety (VAS-A)
Secondary outcomes	
1. Stress level	Saliva cortisol test
	Mean Heart rate
2. Postoperative pain	Visual Analog Scale for pain (VAS-P)
3. Patient satisfaction	Leiden Perioperative Patient Satisfaction Questionnaire (LPPSQ)
4. Hospital Length of Stay (LOS)	Date of admission to the hospital from the date of discharge
5. Adverse effect of VR intervention	The Virtual Reality Symptom Questionnaire (VRSQ)

	S	TUDY P	PERIOD					
	Pre-admission	Preo	perative	ohase	Postoperative phase		Discharge	
TIMEPOINT**	-t 1	t o	t 1	t 2	t 3	t4	t 5	
ENROLMENT:								
Eligibility	х							
Informed consent	Х							
screen: using APAIS		Х						
Allocation		Х						
INTERVENTIONS:								
VR exposure				х				
ASSESSMENTS:								
Primary outcome:			x	Х	x			
Perioperative anxiety								
Secondary outcomes:			x	Х	x			
Stress level								
Postoperative pain			х		x			
Patient satisfaction						Х		
Length of hospital stay							X	
Virtual reality adverse effect				Х				

\*\*- $t_1$ : pre-admission; t0: on admission; t1: on admission to preoperative area; t2: immediately before surgery (holding area); t3: one-hour post-surgery; t4: after 24 hours post-surgery and before discharge; t5: discharge.

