### SECREEING

Patients who meet the above inclusion criteria will be screened for their anxiety level using a validated tool which is The Amsterdam Preoperative Anxiety and Information score (APAIS) (Boker et al., 2002; Laufenberg-Feldmann & Kappis, 2013). The PhD candidate will apply the Amsterdam Preoperative Anxiety and Information score (APAIS) on the day of their surgery in the preoperative holding area. Patients with moderate to high level of preoperative anxiety - defined as a preoperative anxiety score ≥11 (Song et al., 2019) - will be included.

The APAIS is a rapid and clinically practical assessment tool developed by Nelly Moerman and previously validated against other scales to evaluate patients' preoperative anxiety with good sensitivity and strong specificity for clinically significant anxiety (Boker et al., 2002; Laufenberg-Feldmann & Kappis, 2013). It consists of six questions in total. Each question is rated on a five-point Likert scale from 1: "not at all" to 5: "extremely". The sum of scores from questions 1, 2, 4, and 5

show the anxiety level. The sum of scores from questions 3 and 6 show the level of information required by each individual regarding the anesthesia and surgical procedure. A patient with a score of 11 or more (scoring range from 4 to 20) on the anxiety scale experiences moderate to severe anxiety requiring further intervention (Berth, Petrowski, & Balck, 2007; Boker et al., 2002; Laufenberg-Feldmann & Kappis, 2013). On the need for information scale, patients scoring 2 – 4 are categorised as having little and no need for information, patients scoring 5 – 7 are categorised as having an average need for information and the patients scoring 8 – 10 are considered as having high need for information(Berth et al., 2007; Laufenberg-Feldmann & Kappis, 2013).

Amsterdam Preoperative Anxiety and Information score (APAIS)(Berth et al., 2007):

Questions:	1	2	3	4	5
1- I am worried about the anesthetic					
2- The anesthetic is on my mind continually					
3-I would like to know as much as possible about the anesthetic					
4- I am worried about the procedure					
5-The procedure is on my mind continually					
6- I would like to know as much as possible about the procedure					

1:Not at all, .2:Somewhat, 3:Moderate, 4: Moderately high, 5:Extremely

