### ALLOCATION CONCEALMENT

Sealed opaque envelopes organised in numbered sequential order will be used to conceal the treatment allocation. Following screening, potential participants with moderate to high levels of

anxiety will be allocated to the treatment group (either intervention or control) contained in the next envelope.

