# **PRIMARY OUTCOME**

Perioperative anxiety as measured by the visual analog scale for anxiety (VAS-A).

The visual analog scale for anxiety (VAS-A) is valid, reliable, and frequently used for evaluation of perioperative anxiety that allows detection of high anxiety levels in the various surgical group

(Kindler, Harms, Amsler, Ihde-Scholl, & Scheidegger, 2000). The VAS-A consists of a 100 mm horizontal line that represents two behavioral extremes at either end of the continuum (i.e., 'not at all anxious' = 0, whereas 'extremely anxious' = 100). Potential participants will be asked to rate their level of anxiety on the VAS-A tool at three-time points in the study. On admission to the preoperative area (T1), immediately before surgery (T2), and one hour after surgery (T3). Scores on the VAS-A of 25 or higher are said to reflect significant levels of anxiety (Kindler et al., 2000). The primary outcome will be collected by a Research Assistant at the research site, King Abdulaziz University Hospital.

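### The protocol contradicts itself on whether allocation precedes T1, the only possible baseline for the primary model; in the schedule's order the adjusted effect is open to bias

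*Protocol*

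**What the plan says.** **Schedule (Summary of Outcomes Variables and Measures).** The row "screen: using APAIS" and the Allocation row each carry one mark, both at t0. Anxiety, stress and pain are first marked at t1, and VR exposure at t2. The footnote defines these columns as "t0: on admission; t1: on admission to preoperative area; t2: immediately before surgery (holding area").

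**Screening and Allocation Concealment.** The APAIS is applied "on the day of their surgery in the preoperative holding area". Allocation comes next: "Following screening, potential participants with moderate to high levels of" anxiety are assigned from the next numbered envelope. Neither section mentions T1.

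**Primary Outcome and Statistical Plan.** VAS-A is self-rated three times: "On admission to the preoperative area (T1), immediately before surgery (T2), and one hour after surgery (T3"). The fixed effects of the mixed model include "the interaction between treatment and time, and the baseline value of the outcome variable". The same model serves the continuous secondary outcomes that are measured repeatedly.

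**Blinding.** "The Research Assistant involved in outcome data collection will be blinded to the group allocation, as will the statistician" who analyses the data. Participants are not listed as blinded, and the section accepts that they may tell clinicians their arm.

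**The concern.** Adjusting for a baseline score is safe because a value recorded before randomisation cannot be affected by the arm. A value recorded afterwards loses that protection. Here the score is a self-rating of anxiety, and being told that one will or will not receive an intervention meant to relieve anxiety could itself move it. A blinded assistant who collects the form does not protect against that.

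The primary between-group difference at T2 and T3 is at stake. Cortisol and heart rate use the same time points and model, but they are affected only if anticipation alters them physiologically. A larger sample would not remove a bias of this kind, and a later analysis plan could not change when T1 was collected.

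**Working it through.** **1. The plan's own figure.** The Sample Size section gives 150 patients for 0.5 SD, 80% power, 5% type 1 error and 15% dropout. Taking the test as two-sided (the protocol does not say): n per arm = 2 × (1.96 + 0.84)² / 0.5² = 62.7, so 63. Then 63 / 0.85 = 74.1, so 75 per arm and 150 in total. The figure reproduces and does not depend on the present point.

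**2. The order, side by side.**

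| Source | Screening and allocation | First VAS-A | Implied order |
|---|---|---|---|
| Schedule and footnote | t0 | t1 | allocation, then T1 |
| Screening and Allocation Concealment, read with the footnote's locations | holding area, the t2 location | t1, on arrival in the preoperative area | T1, then allocation |
| Screening and Allocation Concealment, if the preoperative and holding areas are one place | holding area | same place | not stated |

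**3. Which value is the baseline.** VAS-A is taken only at T1, T2 and T3. VR is scheduled at t2, and T2 and T3 are the follow-up comparisons. T1 is therefore the only candidate for the baseline covariate, although no section labels it so.

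**4. Bias formula.** Let d be the part of the T1 difference (VR minus control) caused by knowing the arm, and b the coefficient of baseline in the model. Then:

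bias in the adjusted VR-minus-control difference = −b × d

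If d = 0 there is no bias. A T1 lowered in the VR arm by relief, or raised in controls by disappointment, gives d < 0 and biases against VR. A T1 raised in the VR arm gives d > 0 and biases in its favour.

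**5. Illustrative size.** The protocol gives no value for b, d or the SD of VAS-A, so all three are assumed.

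- Low end: 0.5 × 3 = 1.5 mm. High end: 0.7 × 5 = 3.5 mm.
- Against the 20-point target in the Hypothesis section: 1.5 / 20 = 7.5%; 3.5 / 20 = 17.5%.
- Against 0.5 SD with an assumed SD of 25, that is 12.5 mm: 1.5 / 12.5 = 12%; 3.5 / 12.5 = 28%.

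**6. Check by simulation.** The setting was a single-follow-up ANCOVA with 64 per arm, no true effect, 3,000 runs per setting, and equal SD at baseline and follow-up.

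| Slope | d (mm) | SD (mm) | Formula bias (mm) | Simulated bias (mm) | Type I error |
|---|---|---|---|---|---|
| 0.5 | 0 | 20 | 0 | −0.04 | 5.3% |
| 0.5 | −5 | 20 | +2.5 | +2.52 | 12.9% |
| 0.5 | −5 | 40 | +2.5 | +2.70 | 7.4% |
| 0.7 | −5 | 20 | +3.5 | +3.48 | 26.7% |
| 0.7 | +5 | 20 | −3.5 | −3.37 | 25.3% |

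With d = 0, type I error stayed between 4.5% and 5.3% over slopes of 0.3 to 0.7 and SDs of 20 and 40. The formula holds, and the damage depends wholly on whether a shift occurs and how large it is.

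**The case against.** A reader might infer from the schedule that the baseline is definitely collected after patients know their arm, and that the adjusted analysis is therefore invalid. The documents do not support that, for three reasons.

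- **The order is not settled.** Read with the footnote's locations, the Screening section puts T1 before screening and allocation. On that reading T1 is a proper pre-randomisation baseline.
- **Disclosure is not described.** Allocation Concealment says when the envelope is used, not when the patient learns the result. The Blinding section implies that patients may know their arm at some stage, not that they know it at T1.
- **Bias needs a shift.** Even in the schedule's order, T1 comes before VR exposure. Without an effect of knowing the arm on T1 the bias is zero, and the protocol offers no evidence of such an effect.

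It is also fair to say that the size is assumed throughout, that the direction is open (some plausible shifts are conservative), and that a mechanism based on self-rating does not carry over by itself to saliva or sensor readings.

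All of this stands, and it limits the claim to a contradiction with a conditional risk. It does not remove the order shown in the schedule, the conflict with the Screening section, or the lack of any rule that T1 must be recorded before the envelope is opened.

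**Conclusion.** The point holds as an internal contradiction that leaves the primary analysis exposed. The schedule puts allocation before T1, while the body text can be read the other way. In the schedule's order, the covariate of the primary model is a self-rated value taken after randomisation from unblinded patients, so it is no longer protected by randomisation. That is a risk to validity and not a demonstrated bias.

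On assumed values the bias would be 1.5 to 3.5 mm in either direction: modest against the 20-point target, larger against 0.5 SD if the SD is 25. The risk is chiefly to VAS-A. The sample size is unaffected. The point should be settled before recruitment, because the timing of T1 cannot be corrected afterwards.

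**What to change.** State one order in the Screening, Allocation Concealment, Primary Outcome and Secondary Outcomes sections and in the schedule:

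1. APAIS screening and all T1 measurements (VAS-A, VAS-P, saliva, heart rate) are completed.
2. The envelope is opened only once T1 is recorded, with this stated as a rule in Allocation Concealment.
3. VR or standard care follows, then T2.

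Move the Allocation mark to after t1, name T1 as the baseline in the Statistical Plan, and give one screening location in both the Screening section and the footnote.

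The cost is small but not zero. The PhD candidate screens and a blinded research assistant collects T1, so the two need a same-day hand-off before the envelope is opened, and one of the two steps may have to change place. Sample size and model stay as they are.
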